2.2 Analysis sets

Randomized set

All patients who are enrolled in the PK run-in cohort or randomized in Parts A and B. Unless otherwise specified, misrandomized patients will be excluded from the randomized set. For the PK run-in part, this set includes all patients with informed consent and treated with study medication.

Misrandomized patients, if identified from IRT, include patients who are screen-failures, but have been randomized by the investigator before eligibility was finally assessed or mistakenly, and have not been treated. If patients were re-screened and successfully randomized, they will be included in the randomized set according to the treatment assigned in the last randomization.

Note: There is no randomization in the PK run-in cohort. For this cohort, the more appropriate terminology is “Enrolled set”. However, ‘Randomized set’ is used for simplicity.

Full analysis set (FAS)

FAS will be comprised of all patients from Randomized set who take at least one dose of study treatment during the treatment period and whose baseline *P. Falciparum* asexual parasitemia count is greater than 0. Following the intent-to-treat principle, patients will be analyzed according to the treatment group assigned to at randomization.

Safety set (SAF)

Safety set includes all patients who take at least one dose of study drug during the treatment period. Patients will be analyzed according to treatment received. In particular, patient will be

analyzed in the same treatment group as randomized if s/he receives at least one dose of the study medication of that group.

Per-protocol set (PPS)

Per-protocol set will be comprised of patients in FAS who

- did not have any important protocol deviations
- took at least 80% of randomized study medication(s). If a patient vomited the original dose but did not vomit the replacement dose, the patient is considered as taking the dose of study medication. Since a partial compliance, such as 83%, etc., can be calculated based on the actual dosage taken (see Section 2.4.1), this allows patients assigned to KAF156 and LUM-SDF arms to take partial dosages which slightly deviates from the protocol.
- did not take non-study drug antimalarial medications prior to Day 29 unless experiencing any treatment failure (ETF, LCF, LPF) (e.g new infections between Day 8 and Day 29), and
- met at least one of the following criteria: (a) classified as treatment failure (including parasite not cleared) before Day 8 (see [Section 2.1.1](#)), (b) absent from parasitemia at Day 29 or later, (c) had valid PCR evaluations at baseline and at the time point with parasitemia using malaria blood film if parasitemia is present between Day 8 and Day 29, or (d) had parasitemia present on Day 8 or later without parasite clearance before Day 8.

Important protocol deviations for exclusion from PPS are specified in [Table 5-9](#) and will be identified by the clinical team before database lock for each part.

PK analysis set

All patients in the safety analysis set who had evaluable pharmacokinetic parameter data and with at least 80% compliance to study medication and did not receive the concomitant prohibited medication which found to be change in the exposure that impacts interaction in PK parameters.

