### **5.6.6 Rescue medication**

The following circumstances warrant discontinuation of study treatment and the implementation of rescue medication (see [Section 6.5.8](#)):

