#### **Early Treatment Failure (ETF)**

- Development of danger signs or severe malaria on Day 2, Day 3, Day 4 in the presence of parasitaemia.
- Parasitaemia on Day 3 higher than Day 1 count irrespective of axillary temperature
- Parasitaemia on Day 4 with axillary temperature  $\geq 37.5^{\circ}\text{C}$

- Parasitaemia on Day 4 equals to or more than 25% of count on Day 1

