#### **Late Parasitological Failure (LPF)**

- Presence of parasitaemia on any day from Day 8 to Day 43 and axillary temperature  $< 37.5^{\circ}\text{C}$  without previously meeting any of the criteria of Early Treatment Failure or Late Clinical Failure

Commencement of rescue medication with a combination antimalarial product (local standard at the discretion of the investigator or a medically qualified person) may occur after start of trial medications and up to 43 days after the last dose of KAF156/LUM-SDF as deemed necessary by the investigator. Lumefantrine-based treatment must be avoided in case of early treatment failure (ETF). Patients will be monitored, either in clinic, by telephone, or via home visits for three days to ensure adherence to the rescue medication therapy. These patients will not be replaced and will not discontinue the study (i.e., all the examinations as per the assessment schedule and all CRF pages for this patient will need to be completed).

Safety blood tests (Full Blood Count (FBC) and Blood chemistry) will be collected on the initial day of rescue medication dosing. Blood films and blood sampling for parasite count and genotyping must be taken before giving the established anti-malarial treatment.

Patients treated with at least one dose of trial medications will continue to be followed-up until Day 43 according to schedule.

Use of rescue medication (including exact rescue regimen and route of administration) must be recorded on the Concomitant medications/Significant non-drug therapies after start of study drug.

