5.7 Rule of exclusion criteria of analysis sets

Table 5-10 Protocol deviations and non-PD criteria leading to exclusion from analysis sets

Analysis Set	PD (Description and ID) that causes Patients to be excluded	Non-PD criteria that cause Patients to be excluded
Randomized	
 Informed Consent for study participation or parental consent not obtained and patient entered trial (INCL01) 	
 Not randomized (Parts A and B) Misrandomized if identified from IRT (Parts A and B) Not treated with study medication (PK run-in part)
FAS	NA	
 Not in Randomized set; Baseline parasitemia count is 0 or missing No study drug taken
PPS	
 Parasite specie is other than Plasmodium falciparum OR mixed infection (INCL04) Baseline plasmodium falciparum parasite count <1000/uL or >=150000/uL at screening visit (INCL05) No fever within the past 24 hours at baseline (INCL07) Prohibited non-antimalarial medications that may have effect on efficacy (PROH01b) if received before the Day 29 visit without being treatment failures 	
 Not in FAS; <80% of randomized study medication taken Received non-study concomitant antimalarial drugs prior to Day 29 without experiencing treatment failure Not classified as non-responder before Day 8, no positive blood smear parasite on Day 8 onwards, and blood smear parasite result is missing at Day 29 and later (early discontinued) Not classified as non-responder before Day 8, have at least one positive blood smear parasite result between Day 8 and Day 29 which cannot be determined as recrudescence or new infection based on PCR genotyping and have parasites cleared prior to the positive blood smear parasite;

		
 Not classified as non-responder before Day 8, no positive blood smear parasite before Day 29, blood smear parasite result is missing at Day 29, and blood smear parasite result is not negative at Day 43 (intermediate missing)
SAF	NA	
 Not in Randomized set; No study drug taken
PK	Patients who received concomitant prohibited medication which found to be change in the exposure that impacts interaction in PK parameters; will be reviewed case by case for exclusion from the PK set	
 Not in SAF No evaluable pharmacokinetic parameter data Compliance is <80% of randomized study medication taken

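### The per-protocol 80% dosing rule has no exemption for early treatment failure, so a patient in a 2- or 3-day arm whose dosing is stopped for that failure drops out of the primary test

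*SAP*

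**What the plan says.** SAP 2.2 builds the PPS from conditions that must all hold. One is that the patient "took at least 80% of randomized study medication(s"). SAP 5.7, Table 5-10, repeats it as a separate exclusion for less than "80% of randomized study medication taken", with no qualifier. Protocol 9.1 has the same 80% rule, adds that outside the Coartem arm it means every assigned dose, and gives no exemption for failure.

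Other PPS exclusions in Table 5-10 do spare failures:
- Other antimalarials: "Received non-study concomitant antimalarial drugs prior to Day 29 without experiencing treatment failure".
- Prohibited medication that may affect efficacy (PROH01b): "if received before the Day 29 visit without being treatment failures".
- Missing blood smear or undetermined PCR: only patients not already non-responders before Day 8 are excluded.

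The last PPS condition in SAP 2.2 accepts as evaluable a patient "classified as treatment failure (including parasite not cleared) before Day 8". It is one more condition to be met, so it does not waive the 80% rule.

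Protocol 5.6.6 introduces its list of failures, ETF among them, with "The following circumstances warrant discontinuation of study treatment and the implementation of rescue medication". One ETF criterion is "Development of danger signs or severe malaria on Day 2, Day 3, Day 4 in the presence of parasitaemia". SAP 2.1.1.2 makes any ETF a non-responder for PCR-corrected ACPR. SAP 2.5.2 tests each combination on the PPS: the lower limit of the exact two-sided 95% interval must exceed 80%.

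**The concern.** Under-dosing is normally a reason to leave a per-protocol set because the patient did not receive the regimen. Here the under-dosing can be the result of the outcome: the treatment failed, so the remaining doses were not given. Removing that patient deletes a failure because it was a failure, which can only raise the observed response rate.

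The PPS test is the primary analysis. With so few failures allowed per arm, one patient can decide it. The rule also bears unequally on regimens in a trial that compares durations: a 1-day arm cannot lose a patient this way, while 2- and 3-day arms can. The neighbouring exemptions and the evaluability condition suggest that early failures were meant to count, so this looks like an oversight.

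**Working it through.** **1. The plan's own figure.** Inputs from SAP 3 and 2.5.2: 42 PPS patients per arm, null 80%, true rate 95%, exact (Clopper-Pearson) lower limit. The lower limit for x/n is the 2.5% quantile of Beta(x, n − x + 1). It is 80.5% for 39/42 and 77.4% for 38/42, so an arm of 42 passes with at most 3 failures. Power at 95% is 84.3%, which agrees with the stated minimum of 80%. The chance of passing at a true 80% is 2.1%.

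**2. Compliance when dosing is stopped early, on planned doses.**
- 3-day arms: 1/3 = 33% or 2/3 = 67%.
- 2-day arm: 1/2 = 50%.
- Coartem: 4/6 = 67% is excluded and 5/6 = 83% is kept. Coartem is not tested against 80%, so only the exploratory differences are touched.

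**3. Which denominator.** SAP 2.4.1 uses planned doses for the percentage of full doses and forms its below-80% and at-least-80% categories from full doses taken. Only the day-average formula leaves the number of days undefined. On planned days, a 3-day patient stopped after one dose scores (100 + 0 + 0)/3 = 33%. On days actually dosed, the same patient scores 100/1 = 100% and the problem disappears. The reference to randomized medication, and the protocol's requirement of all assigned doses, favour planned.

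**4. Who is affected.** Only patients who meet ETF and are stopped for it before their last planned dose. The main route is danger signs or severe malaria with parasitaemia: on Day 2, or on Day 3 before the third dose, in the 3-day arms; on Day 2 before the second dose in the 2-day arm. The route through a Day 3 count above the Day 1 count is narrow. Under SAP 2.1.1, Day 3 starts at 48 hours for repeated assessments, the nominal time of the third dose, so the film must be read and the dose then withheld.

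**5. One deletion.** 38/42 has a lower limit of 77.4% and fails. Drop one of its four failures: 38/41 has 80.1% and passes.

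**6. Chance of passing if a share q of patients is affected.** q is assumed; the documents give no rate. With true response p, counting these patients as failures, and E ~ Bin(42, q) patients removed:

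P(pass) = Σₑ P(E = e) × P[Bin(42 − e, (1 − p − q)/(1 − q)) ≤ f(42 − e)]

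where the binomial counts the remaining failures and f is the largest number that still passes: 2 for n = 34–40, 3 for n = 41–47.

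| True response p | q = 0 | q = 0.5% | q = 1% | q = 2% |
|---|---|---|---|---|
| 80% | 2.1% | 2.4% | 2.8% | 3.4% |
| 90% | 38.4% | 42.2% | 45.6% | 51.7% |

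These q values are 2.5%, 5% and 10% of all failures at a true 80%, and 5%, 10% and 20% at a true 90%. At a true 80%, the chance of passing reaches the nominal one-sided 2.5% at q = 0.59%. The chance that a 42-patient arm has at least one such patient, 1 − (1 − q)^42, is 19%, 34% or 57%.

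**The case against.** The strongest reply is that these patients cannot go unnoticed. The exact FAS analysis (SAP 2.5.4) counts them as non-responders, and the FAS Kaplan-Meier analysis (2.5.4.1) counts them as events. The proportion with ETF is a secondary endpoint on the FAS, with an exact interval per arm (2.7.1, 2.7.2.2). The interim assessment after Part A covers all adverse and serious adverse events (2.15), and danger signs and severe malaria are recorded as adverse events (2.1.1.1). The DMC receives ETFs on the safety set at periodic reviews and at the end of Part A (Table 2-8), and protocol 8.4 lets it recommend stopping a cohort for an unacceptable ETF rate. All of this stands. It makes the loss visible but leaves the primary PPS test computed without these patients.

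A reader might infer that every ETF leaves the PPS. The documents do not support that. ETFs on Day 4, ETFs in the 1-day arms and ETFs who completed dosing all stay in. The last group can exist because rescue may start "up to 43 days after the last dose of KAF156/LUM-SDF as deemed necessary by the investigator", and because the SAP derives ETF from films, temperatures and adverse event dates.

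A reader might also infer that the entry rule for Part B is expressly a PPS rule. Protocol Table 3-2 names no analysis set. PPS is the likely reading, because the same criterion is the primary PPS test and Table 2-8 gives Day 29 cure rates on the PPS, but it remains an inference. Table 3-2 also sets a separate safety hurdle.

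**Conclusion.** The point holds in this limited form and should be fixed. As written, the 80% rule removes from the primary test any patient in a 2- or 3-day KAF156/LUM-SDF arm who is stopped for ETF before the last planned dose, although the SAP defines that patient as a non-responder. This rests on compliance being computed on planned doses or days, which the text favours but does not settle for the day-average formula.

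The direction is certain: any bias is upward. The size is not. With no such patient in an arm there is no effect, and at an assumed 0.5% the test still keeps its nominal level. The documents therefore do not support saying that the error rate is in fact inflated. They support saying that the rule permits it, and that one deletion can reverse an arm's result.

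**What to change.** In SAP 2.2 and Table 5-10, state that the below-80% exclusion does not apply to patients who met ETF criteria before their last planned dose and whose remaining doses were not given because of that ETF. They stay in the PPS as non-responders. Carry the same sentence into protocol 9.1 at the next amendment.

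State the precedence. Repeated vomiting is itself a danger sign, so a patient who meets the SAP-derived ETF definition by the time dosing stopped, and is stopped for it, is exempt even if that sign was vomiting. Patients under-dosed for any other reason stay excluded whatever their later outcome. Keeping those only when they fail would bias the other way. If a share r = 5% were under-dosed for other reasons, the expected rate would be p(1 − r)/[(1 − r) + r(1 − p)]; a true 80% would read 0.76/0.96 = 79.2%.

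State in SAP 2.4.1 that the day-average compliance divides by planned days.

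The SAP change is a few sentences and one programming condition, with no new data: protocol 5.7.2 already has the primary reason for stopping recorded on the Treatment Completion eCRF. That reason is chosen by the investigator in an open-label trial, so it should be used together with the derived ETF status. The protocol change needs the approvals in protocol 11.1.

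The SAP log already has an entry after the final database lock. If the database is locked, leave the primary PPS as it is and report this version as a labelled post hoc sensitivity PPS, with per-arm counts of patients whose status differs. It partly overlaps the FAS analysis, but keeps the other PPS exclusions and so isolates the effect of this one rule.

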## Per-protocol set (PPS)

Per-protocol set will be comprised of patients in FAS who

- did not have any important protocol deviations
- took at least 80% of randomized study medication(s). If a patient vomited the original dose but did not vomit the replacement dose, the patient is considered as taking the dose of study medication. Except for patients who are assigned to Coartem® cohort, this requires that all patients take all KAF156 and LUM-SDF dosages as assigned
- did not take other antimalarial medications prior to Day 29 for reasons other than rescue medication given for signs and symptoms of infection with *P. falciparum* or unsatisfactory therapeutic effect, and
- met at least one of the following criteria: (a) classified as treatment failure before Day 8 (see [Section 6.5.8](#)), (b) absent from parasitaemia at Day 29 or later, or (c) had valid PCR evaluations at baseline and at the time point with parasitaemia if parasitaemia is present at Day 8 or later.

Important protocol deviations for exclusion from PPS will be identified by the clinical team before database lock for each part.

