2.1.1.2 Definition of ACPRs

Uncorrected ACPR at Day X where X=15, 29, or 43

- A patient is considered as non-responder at Day X if the patient experiences an ETF, LCF from Day 5 to Day X, or LPF from Day 8 to Day X.
- A patient is also considered as non-responder if the parasite is not cleared by Day X unless the patient discontinues the study prior to Day X without ETF or LCF or LPF, in which case the response is considered as missing.
- A patient is considered as responder (Uncorrected ACPR) at Day X if the patient is not classified as a non-responder at Day X and the patient has a malaria blood film showing absence of parasite at Day X or later if Day X is missing.
- The response for a patient is considered as missing/underdetermined if the patient is not classified as a non-responder and the malaria blood film result at Day X is missing and not followed by a subsequent negative result.

PCR-corrected ACPR at Day X where X=15, 29, or 43

- A patient is considered as non-responder at Day X if the patient experiences an ETF or LCF from Day 5 to Day 7.
- A patient is also considered as non-responder if the parasite is not cleared by Day X unless the patient discontinues the study prior to Day X without ETF or LCF or LPF, in which case the response is considered as missing,
- A patient is considered as non-responder at Day X if the patient has a parasite recrudescence from Day 8 to Day X
- A patient is considered as responder (corrected ACPR) at Day X if the patient is not classified as a non-responder by Day 7 and has a new infection or negative results from Day 8 to Day X based on PCR genotyping unless that the patient did not have parasites cleared prior to the new infection, in which case the patient is considered as non-responder.
- A patient is considered as responder at Day X if the patient is not classified as a non-responder at Day X and the patient has a malaria blood film showing absence of parasite at Day X or later if Day X is missing.
- The response for a patient is considered as missing/underdetermined if
 - The patient, not classified as non-responder at Day X, has parasite present from Day 8 to Day X for which the PCR genotyping of recrudescence or new infection is not determined.
 - The patient is not classified as a non-responder at Day X and the malaria blood film result at Day X is missing and not followed by a subsequent negative result.

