Note - The outcome of PCR-corrected ACPR and uncorrected ACPR at a given day is categorized as responder or non-responder to distinguish from failure used in early treatment

failure, late clinical failure or late parasitological failure. With this notation, ACPR rate is the proportion of responders.

Recurrence of parasitemia after 7 days is considered as non-responder for uncorrected ACPR. We reclassify such patient as responder for PCR-corrected ACPR if recurrence of parasitemia after 7 days is due to new infection. Whether the recurrence of parasitemia after 7 days is due to recrudescence or new infection is determined and provided by the central laboratory. Negative PCR will categorize the patient as PCR corrected responder.

The above definitions of ACPRs are purely based on the malaria blood film and PCR results without consideration for taking concomitant anti-malaria drugs. In statistical analyses, some responses may be overridden for patients who take concomitant anti-malaria drugs (see [Sections 2.5 and 2.7](#)).

Fever Clearance is defined (in patients with axillary temperature of $\geq 37.5^{\circ}\text{C}$ at baseline) as the time of the first measurement of at least 2 consecutive axillary temperatures of $< 37.5^{\circ}\text{C}$ (or $< 38.0^{\circ}\text{C}$ for alternative routes) measured at least 24 hours apart.

Time to parasite clearance (PCT) is defined as time from the first dose until the first total and continued disappearance of asexual parasite forms which remained at least a further 48 hours

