5.1.4 Visit windows

When visit windows are used, all visits will be re-aligned, i.e., they will be mapped into one of the visit windows. E.g., if the Day 4 visit of a patient is delayed and occurs on Day 7, say, it will be re-aligned to visit window Day 8. In the case of major deviations from the visit schedule, or due to unscheduled visits, several assessments of a patient may fall in a particular visit window (either scheduled or unscheduled). Statistical approaches to handle multiple assessments in a given visit window are specified below.

- Of note, patients are allowed to have gaps in visits. All data collected will be displayed in listings.
- Lower limit and upper limit of the Day 29 visit is set to be Day 25 and Day 33 respectively, according to the protocol visit schedule since this is the primary analysis timepoint.
- The following rules are used to determine the window for other visits post baseline:
 - “Lower limit” = “upper limit of prior applicable visit” + 1.
 - “Upper limit” = “target day of current visit” + integer part of (“target day of next applicable visit” – “target day of current visit”)/2 with the exception of Day 29
 - No upper limit for Day 43 visit
 - Upper limit of Day 15 is one day before the lower limit of Day 29

For assessments that are scheduled to be performed only once on a day, [Table 5-5](#) describes the analysis windows mapping to visits (not just scheduled visits) based on study days alone. For the assessments that may be performed on multiple timepoints on a day, [Table 5-6](#) describes the analysis windows mapping to visits based on study day and time. Repeat and/or unscheduled visits (which will be numbered in the database according to new NCDS standards) will be mapped for analysis purposes in the same way. If there are multiple measurements within an analysis window, the conventions defined in [Table 5-7](#) will be used to determine the appropriate measurement to be selected for analysis.

The mapped visits will be used in the by visit analyses. However, the listings will show the collected data regardless of used in the by visit analyses.

Table 5-5 Analysis visit windows based on study days alone

Analysis Visit	Target Day	Analysis window for assessment group		
		Vital signs/ Hematology/	Chemistry/ Urinalysis	Thyroid function
Baseline	1	Up to Day 1	Up to Day 1	up to day 1
Day 2	2	Day 2	NA	NA
Day 3	3	Day 3	NA	NA
Day 4	4	Day 4	NA	NA
Day 5	5	Days 5 - 6	NA	NA
Day 8	8	Day 7 - 11	NA	NA

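### The per-protocol antimalarial screen stops at Day 29, but a missing Day 29 film can be replaced by a later one, so a film cleared by a non-study drug can count as cure

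*SAP*

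**What the plan says.** SAP 2.2 admits to the PPS patients who "did not take non-study drug antimalarial medications prior to Day 29 unless experiencing any treatment failure (ETF, LCF, LPF". Table 5-10 (SAP 5.7) gives the matching exclusion: "Received non-study concomitant antimalarial drugs prior to Day 29 without experiencing treatment failure". The cut-off comes from protocol 9.1, which requires that patients "did not take other antimalarial medications prior to Day 29 for reasons other than rescue medication".

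The response has a different clock. SAP 2.5.3 accepts any film from Day 25 to Day 33 as the Day 29 assessment. If there is none, SAP 2.1.1.2 accepts a "malaria blood film showing absence of parasite at Day X or later if Day X is missing". PPS criterion (b) in SAP 2.2 likewise accepts absence of parasites at Day 29 or afterwards. The intermediate-missing row of Table 5-10 drops a patient with no Day 29 film only if the Day 43 film is not negative. For that last window, SAP 5.1.4 states: "No upper limit for Day 43 visit".

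SAP 2.1.1.2 also says that its response definitions are "purely based on the malaria blood film and PCR results without consideration for taking concomitant anti-malaria drugs", and leaves any override to SAP 2.5 and 2.7.

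**The concern.** The PPS rule is there so that the primary rate reflects cure by the study drug. It does this only if the screen for other antimalarials covers the whole time up to the film that supplies the answer. Here the screen ends at Day 29, while the fallback film can be about two weeks later. A recrudescence that no study film caught, and that another drug then cleared, would be credited to the study arm. In Part A the lower limit of this rate is the efficacy criterion for carrying a regimen into Part B (protocol Table 3-2).

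**Working it through.** **The plan's own figure.** Inputs from SAP 2.5.2 and 3: null rate 80%, lower limit of the two-sided 95% Clopper-Pearson interval, 42 PPS patients per arm, power at least 80% at a true rate of 95%. The lower limit for x responders in n is the 0.025 quantile of Beta(x, n - x + 1). The smallest passing count at n = 42 is 39. Then P(Bin(42, 0.95) >= 39) = 0.843 and P(Bin(42, 0.80) >= 39) = 0.0208. The power statement reproduces and is not affected by this point.

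**Tracing one patient through the rules.** Suppose the initial infection clears, there is no film on Days 25-33, an antimalarial is taken outside the study on Day 33 with no study film beforehand, and the Day 43 film is negative.

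- PPS antimalarial rule: Day 33 is not before Day 29, so the patient is not excluded.
- PPS criterion (b): met by the Day 43 film.
- Intermediate-missing row of Table 5-10: not triggered, because the Day 43 film is negative.
- Treatment failure (SAP 2.1.1.1): every category needs parasitaemia, and none was recorded.
- Response (SAP 2.1.1.2): no failure and a later negative film, so a PCR-corrected responder.

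**Looking for an override.**

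- SAP 2.5.2 and 2.5.3 contain none for the PPS.
- The handling rules in SAP 2.5.4 are for patients outside the PPS, and they ignore a non-rescue antimalarial.
- The sensitivity analysis in SAP 2.7.2.2 that counts antimalarial users as non-responders is for uncorrected ACPR in the FAS and also stops before Day 29.
- The FAS Kaplan-Meier analysis (SAP 2.5.4.1) censors at non-rescue antimalarial use. Here that date is on or after Day 29, so the patient is still event-free where the curve is read.

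**Second route, under one reading only.** If Day 29 means the calendar day, a drug taken on Day 30 before a Day 29 visit film on Day 32 also passes the screen.

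**Effect on the decision.** Clopper-Pearson lower limits against 80%:

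| Responders / n | Lower limit | Result |
|---|---|---|
| 39/42 | 80.5% | pass |
| 38/41 (one excluded from 39/42) | 80.08% | pass |
| 37/40 (two excluded from 39/42) | 79.6% | fail |
| 38/42 (one recoded as non-responder) | 77.4% | fail |

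At n = 41, the minimum size named in SAP 3, the pass mark is 38. Excluding one such responder turns 38/41 (pass) into 37/40 (fail).

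**Effect on error rate, with an assumed frequency.** Let k of 42 patients count as responders whatever the study drug did, and let the others have a true rate of 80%. The chance of passing is P(Bin(42 - k, 0.80) >= 39 - k): 0.0208, 0.0244, 0.0285 and 0.0332 for k = 0, 1, 2 and 3, against a nominal 0.025. The values of k are assumptions.

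**The case against.** The strongest reply is that the chain of events is long and the plan works against it. Patients are told to contact the investigator if symptoms return (protocol 3.1). Films and genotyping samples must precede rescue treatment (5.6.6), and new medications must be reported and recorded (5.6.7). This stands as an argument that cases will be few. The documents give no frequency, so a reader who infers that missed visits with outside treatment are a common pattern goes beyond them.

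Second, Day 29 may mean the analysis visit, as SAP 2.5.3 suggests. The neighbouring rule for prohibited non-antimalarials (PROH01b) says "if received before the Day 29 visit without being treatment failures", and SAP 2.7.2.2 uses the two phrasings side by side. On that reading the Day 29-33 route closes, and so does any disagreement between the two rows of Table 5-10, so a flat contradiction in that table is not established. The missing-film route stays open.

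Third, protocol 5.6.8.1 bars antimalarials for the whole study, so such use could be flagged as an important deviation. But Table 5-10 lists no antimalarial deviation, and SAP 2.2 points for deviations to Table 5-9, which is the list of prohibited drugs.

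Fourth, the patient may be classed correctly. Someone who falls ill on Day 33 may have been parasite-free on Day 29, and a new infection counts as a response anyway. This stands: only an undetected recrudescence is wrongly credited.

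Finally, the open-ended Day 43 window is a mapping convention. The visit itself is scheduled at Day 43 plus or minus 4 days (protocol Table 6-2).

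**Conclusion.** The gap is real but narrow. Followed to the letter, the plan keeps in the primary set, as a cure, a patient whose only qualifying film came after a non-study antimalarial. This is certain for the missing-film route and depends on the meaning of Day 29 for the other. Any bias is upward, and its size is unknown and probably small.

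Two stronger readings are not supported. One is that a single such patient decides an arm at n = 42. That compares 39/42 with 38/42, which recodes the patient as a failure; a per-protocol remedy excludes the patient, and 38/41 still passes. It takes two in one arm at 42, or one at 41, and only for an arm at the pass mark. The other is that the reverse case is an error: a negative film on Day 25, an antimalarial on Day 27, and exclusion. Removing a patient who took a barred drug before Day 29 is an ordinary, conservative per-protocol exclusion.

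The point merits correction because it touches the primary test and is cheap to close, not because it is likely to overturn the result.

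**What to change.** In the PPS rule of SAP 2.2 and in Table 5-10, replace the Day 29 cut-off with *prior to the blood film used to determine the Day 29 response*, meaning the selected Day 25-33 film or, if that is missing, the later negative film. Use the same wording for PROH01b.

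Leave the response definition in SAP 2.1.1.2 and the FAS rule unchanged. Editing the definition would make these patients missing, and so non-responders, in the FAS, where protocol 9.4.4 and SAP 2.5.4 analyse them as if the drug had not been taken.

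Protocol 9.1 has the same cut-off, so record the change in SAP Section 4, which now reports no changes to the protocol-specified analyses.

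The cost is one date comparison on data already collected. A few patients may leave the PPS, including some who were correctly classed at Day 29, which slightly reduces its size. As a by-product, a patient whose Day 25-33 film preceded the drug would no longer be excluded.
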